- The protocol endpoint "Proportion of participants remaining NEDA-3 during Year 3 Visit Period or Year 4 Visit Period after the initial dose of cladribine tablets among those with NEDA-3 during Year 1 or 2 after initial dose of cladribine tablets" is replaced with "Proportion of participants remaining NEDA-3 ... among those with NEDA-3 during Course 1 Treatment Period or Course 2 Treatment Period in the parent study", as Study Periods in parent study were not defined in calendar years relative to initial dose of cladribine tablets.
- The text "the onset of action of cladribine treatment" in protocol endpoints is replaced with "start of study medication", as these refer to the same day (Day 1 as defined in Section 9.5) and the latter is chosen to keep consistent with parent study Day 1 definition.
- The protocol endpoint "Time from the initial dose of cladribine tablets to treatment start with other DMDs" is removed. This is because in the parent study, a participant receiving any rescue medication with any other DMD would not participate further in any trial assessments and should instead complete the early termination visit for final assessment. Such participants would not have EDSS or MRI assessment at M24 Visit and therefore would not be included in the Extension Study as per inclusion criteria. Hence, the Extension Study population have excluded potentially a subgroup of participants who started DMDs earlier during the parent study. The analysis of "time from initial dose of cladribine to treatment start with other DMDs" conducted on the Extension Study population would be biased and, therefore, would not be performed.
- The protocol endpoints "time from extension study baseline to ..." are replaced with "Time from M24 Visit in the parent study to ...". This is because the Extension Study baseline is planned to coincide with the parent study last visit (M24 Visit), while in practice it can occur after the parent study last visit and before Visit 1, resulting in incomparable starting dates across participants for the planned time-to-event analyses in protocol. These time-to-event analyses will be more meaningful to start from the intended Extension Study baseline, i.e., M24 Visit in the parent study.
- The protocol endpoints, "time from ... to second qualifying relapse" are replaced with "time from ... to recurrent qualifying relapses". Correspondingly, a recurrent event analysis will be implemented as specified in Section 14.2.3.

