8.1 Definition of Analysis Sets

Enrolled Set (ES)

All participants who provided informed consent.

Full Analysis Set (FAS)

The FAS will include all enrolled, eligible participants.

Safety Analysis Population (SAF)

All participants treated with at least one dose of cladribine tablets during the parent study.

Treatment Completer Set (TCS)

All participants from the FAS who completed the full treatment course of the first and second year in the parent study (i.e., participants who were in TCS-2 as defined in MAGNIFY MS IAP version 3.0).

Analyses per Analysis Set

Unless otherwise specified, all efficacy analyses will be performed on the FAS and all safety analyses will be performed on the SAF. The primary analysis will also be repeated on the TCS as a sensitivity analysis.

If not stated otherwise, disposition of participants will be summarized on the ES, previous and concomitant medications will be summarized on the FAS, and the analyses on demographics and other baseline characteristics will be based on the FAS.

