Concomitant procedures which were undertaken any time during the Extension Study Period will be listed by participant for the SAF.

13 Study Intervention: Compliance and Exposure

As no treatment is provided in the Extension Study, participants' compliance and exposure in the MAGNIFY MS trial will be presented for the Extension Study SAF as defined in MAGNIFY MS IAP version 3.0.

14 Efficacy Analyses

The following analyses will be performed based on the FAS except when otherwise stated.

For the detailed definition of covariates and stratification factors that are used in the statistical models see Section 9.10. Details about the derived MRI endpoints and general handling of MRI data is described in Section 9.8.

Descriptive summary statistics will be presented for the absolute values and the changes from Baseline as applicable by Visit [Protocol Scheduled Visits except for Baseline (defined in Section 9.1)] for all efficacy endpoints (and the components, where applicable) for the FAS and respective subgroups for which the variables are analyzed. Details about the presentation of continuous and categorical variables are given in Section 9.

Wherever possible, all estimated results from the statistical models will be calculated with the same observed margin which reflects the population of the whole corresponding analysis set, regardless of missing data (as described in MAGNIFY MS IAP version 3.0).

14.1 Primary Endpoint: Proportion of participants with No Evidence of Disease Activity (three parameter [NEDA-3]) during Year 3 Visit and Year 4 Visit Period after the initial dose of cladribine tablets

The primary endpoint for the Extension Study is defined as the proportion of participants with NEDA-3 during Year 3 Visit and Year 4 Visit Period after the initial dose of cladribine tablets, i.e., NEDA-3 during the following period will be evaluated:

• Year 3 Visit and Year 4 Visit Period (i.e., Extension Study Period)

For the detailed definition of Periods, see Section 9.6.

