14.2 Secondary Endpoints

14.2.1 No Evidence of Disease Activity

As a secondary analysis, NEDA-3 during the following Periods (see definition in Section 9.6) will be analyzed similarly as in the primary analysis using the KM method:

Year 3 Visit Period

- Start date: end date of M24 Visit (see definition in Section 14.1.1) + 1
- Event date: same as in Section 14.1.1 accounting for events started during Year 3 Visit Period only
- Censoring date: the minimum of the scan date of the last available MRI during Year 3 Visit Period, the assessment date of the last available EDSS during Year 3 Visit Period, and the end date of Year 3 Visit Period (see definition in Section 9.6)

Year 4 Visit Period

- Start date: end date of M36 Visit + 1
- Event date: same as in Section 14.1.1 accounting for events started during Year 4 Visit Period only

• Censoring date: the minimum of the scan date of the last available MRI during Year 4 Visit Period, the assessment date of the last available EDSS during Year 4 Visit Period, and the Extension Study completion/discontinuation date

After start of study medication until end of Year 3 Visit Period

- Start date: date of Day 1 as defined in Section 9.5
- Event date: The event date will be defined as the minimum of
 - o the onset date of the first qualifying relapses during the Parent and Extension Study Period
 - o the start date of the first 6MCDP during the Parent and Extension Study Period
 - o the scan date of the first MRI during the Parent and Extension Study Period where at least one T1 Gd+ lesion or at least one active T2 lesion (see Section 9.8 for definition) is identified,

accounting for events started during "After start of study medication until end of Year 3 Visit Period" only.

• Censoring date: the minimum of the scan date of the last available MRI during "After start of study medication until end of Year 3 Visit Period", the assessment date of the last available EDSS during "After start of study medication until end of Year 3 Visit Period", and the end date of "After start of study medication until end of Year 3 Visit Period" (see definition in Section 9.6)

After start of study medication until end of Year 4 Visit Period (i.e. Parent and Extension Study Period)

- Start date: date of Day 1 as defined in Section 9.5
- Event date: same as for "After start of study medication until end of Year 3 Visit Period" accounting for events started during "After start of study medication until end of Year 4 Visit Period"

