14.2.2 Time to First Disease Activity

Time to first disease activity is defined as the time to first occurrence of either qualifying relapse, or 6MCDP, or new or enlarging T2-hyperintense lesions (active T2 lesions), or new T1 Gd+ lesions. This will be evaluated for the following Periods with corresponding start dates defined below:

- Extension Study Period
 - Start date for time to first disease activity: end date of M24 Visit + 1 (as defined in Section 14.1.1)
- Parent and Extension Study Period

o Start date for time to first disease activity: date of Day 1 (as defined in Section 9.5)

Since events described above are the same events as in NEDA-3 definition, the event date will be defined the same as in Sections 14.1.1 or 14.2.1, accounting for only events started during the above Periods, respectively. If the participant did not experience any disease event during a Period, the minimum of the scan date of the last available MRI during this Period, the assessment date of the last available EDSS during this Period, and the Extension Study completion/discontinuation date will be used as the censoring date.

Time to first disease activity (in months) will be calculated as [event date or censoring date as applicable – start date of the Period + 1]/30.4375 and the 5%, 10%, 15%, 25% percentile and median time to first disease activity will be estimated using the KM method along with the 95% CI.

Analysis (Analysis Set)	Derivation	Statistical Analysis Methods	Missing data handling
Secondary er	ndpoint: Time from M24 Visit to	o first disease activity	
Secondary (FAS)	Time to event: [event date or censoring date as applicable – start date + 1]/30.4375 for disease activities started during Extension Study Period	KM time-to-event: 5%, 10%, 15%, 25% percentiles and Median time to disease activity will be estimated as per the KM method and reported along with the corresponding 95% CI.	Same as Section 14.1.1
Secondary (FAS by subgroup "Previous treatment with DMDs")	Same as above	Same as above with KM estimates reported by subgroup.	Same as Section 14.1.1
Secondary er	ndpoint: Time from initial dose	of cladribine tablets to first diseas	e activity
Secondary (FAS)	Time to event: [event date or censoring date as applicable – start date + 1]/30.4375 for	Same as above.	Same as above.
Secondary (FAS by subgroup "Previous treatment with DMDs")	disease activities started during Parent and Extension Study Period		

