14.2.3 Time to MRI Activities, 6MCDP, Qualifying Relapse and Treatment Start with Other DMDs

Time (in months) from the initial dose of cladribine tablets (i.e. start date = date of Day 1 as defined in Section 9.5) to the following events will be calculated as [event date or censoring date as applicable – start date + 1]/30.4375, and analyzed similarly as in Section 14.2.2 using the KM method.

- first new or enlarging T2 lesion
 - Event date: the scan date of the first MRI during the Parent and Extension Study Period where at least one active T2 lesion (see Section 9.8 for definition) is identified
 - Censoring date: participants with no active T2 lesion identified at any scans during the Parent and Extension Study Period will be censored at the scan date of the last available MRI during this Period
- first new T1 Gd+ lesion
 - Event date: the scan date of the first MRI during the Parent and Extension Study Period where at least one new T1 Gd+ lesion (see Section 9.8 for definition) is identified
 - Censoring date: participants with no new T1 Gd+ lesion identified at any scans during the Parent and Extension Study Period will be censored at the scan date of the last available MRI during this Period
- first 6MCDP, as measured by EDSS
 - Event date: the start date of the first 6MCDP during the Parent and Extension Study Period
 - 6MCDP during the Parent and Extension Study Period will be defined similarly as in Section 14.1.1 with just Extension Study Period replaced by Parent and Extension Study Period.
 - Censoring date: participants with no 6MCDP started during the Parent and Extension Study Period will be censored at the assessment date of the last available EDSS during this Period
- first qualifying relapse
 - Event date: the onset date of the first qualifying relapse during the Parent and Extension Study Period

 Censoring date: participants with no qualifying relapse reported during the Parent and Extension Study Period will be censored at the Extension Study completion/discontinuation date

Time (in months) from M24 Visit (i.e. start date = end date of M24 Visit + 1) to the following events will be calculated as (event date or censoring date as applicable – start date + 1/30.4375, and analyzed similarly as in Section 14.2.2 using the KM method.

- first new or enlarging T2 lesion
 - Event date: the scan date of the first MRI during the Extension Study Period where at least one active T2 lesion (see Section 9.8 for definition) is identified

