 - Censoring date: participants with no active T2 lesion identified at any scans during the Extension Study Period will be censored at the scan date of the last available MRI during this Period
- first new T1 Gd+ lesion
 - Event date: the scan date of the first MRI during the Extension Study Period where at least one new T1 Gd+ lesion (see Section 9.8 for definition) is identified
 - Censoring date: participants with no new T1 Gd+ lesion identified at any scans during the Extension Study Period will be censored at the scan date of the last available MRI during this Period
- first 6MCDP, as measured by EDSS
 - Event date: the start date of the first 6MCDP during the Extension Study Period (see definition in Section 14.1.1)
 - Censoring date: participants with no 6MCDP started during the Extension Study Period will be censored at the assessment date of the last available EDSS during this Period
- first qualifying relapse
 - Event date: the onset date of the first qualifying relapse during the Extension Study Period
 - Censoring date: participants with no qualifying relapse reported during the Extension Study Period will be censored at the Extension Study completion/discontinuation date
- treatment start with other DMDs

- Event date: the start date of the first other DMDs used during the Extension Study Period
- Censoring date: participants who did not use any other DMDs during the Extension Study Period will be censored at the Extension Study completion/discontinuation date

A recurrent event analysis will be performed on all qualifying relapses using the Mean Cumulative Function (MCF) method, where MCF(t) represents the mean cumulative number of relapses up to time t. The MCF estimate for recurrent events will be calculated and plotted for all qualifying relapses. The MCF Nelson estimates will be presented for every month along with their 95% CIs. The increase in MCF in each month, defined as MCF(t) - MCF(t-1) will also be displayed.

Time (in months) from the initial dose of cladribine tablets (i.e. start date = date of Day 1 as defined in Section 9.5) to each event and to censoring (as defined below) will be calculated as [event date or censoring date – start date + 1/30.4375, and analyzed using the MCF method.

- recurrent qualifying relapse
 - Event date: the onset date of each qualifying relapse during the Parent and Extension Study Period

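### The SAP drops one Day 1 endpoint because rescued participants are selected out of the extension, but keeps eight other Day 1 secondary endpoints on the same selected set with no caveat and no all-treated analysis

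*SAP*

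**What the plan says.** SAP Section 7 explains why the protocol endpoint of time from first dose to another DMD is gone. A parent-study participant given a rescue DMD stopped trial assessments, so would have no M24 EDSS or MRI and would fail the extension's inclusion criteria. The section continues: "Hence, the Extension Study population have excluded potentially a subgroup of participants who started DMDs earlier during the parent study". It concludes that this analysis "conducted on the Extension Study population would be biased and, therefore, would not be performed".

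Protocol Section 5.1 sets the entry condition: parent-study MRI from Month 18 or Month 24, plus EDSS and relapse data from Month 24.

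For efficacy, SAP Section 14 opens with "The following analyses will be performed based on the FAS except when otherwise stated", and Section 8.1 defines that set: "The FAS will include all enrolled, eligible participants". Only the primary analysis is repeated on another set, the Treatment Completer Set, which lies inside the FAS.

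The retained Day 1 endpoints are in three sections:

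- **14.2.1:** NEDA-3 from start of medication to the end of the Year 3 Visit Period and to the end of the Year 4 Visit Period. Events include "the onset date of the first qualifying relapses during the Parent and Extension Study Period".
- **14.2.2:** time to first disease activity over both studies. "Start date for time to first disease activity: date of Day 1 (as defined in Section 9.5").
- **14.2.3:** "Time (in months) from the initial dose of cladribine tablets (i.e. start date = date of Day 1 as defined in Section 9.5") to the first active T2 lesion, first new Gd+ lesion, first 6MCDP and first qualifying relapse. The recurrent-relapse mean cumulative function (MCF) uses "the onset date of each qualifying relapse during the Parent and Extension Study Period".

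**The concern.** A participant enters these analyses only after meeting a condition assessed about two years past the time origin, yet is credited with follow-up from Day 1. By the SAP's own account, rescue with another DMD prevents a participant from meeting that condition. If rescue tends to follow disease activity, the parent-study events of the more active participants are removed selectively and the results from first dose look too favourable.

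The SAP acts on this reasoning for one endpoint and does not mention it for the others. The affected results are the 3- and 4-year figures from first dose, which are likely to be quoted as the long-term effect of treatment. One of them, NEDA-3 from start of medication to the Year 3 Visit, is also reported at the interim analysis (SAP Section 6.1).

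**Working it through.** **Count of affected endpoints (SAP 14.2.1 to 14.2.3).** Two NEDA-3 proportions + one time to first disease activity + four times to a first component event + one relapse MCF = 8. Visible caveats on these eight: none. Visible efficacy analyses on all participants treated in the parent study: none.

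**Safeguards looked for.**

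- Protocol Section 9.4.1 allows secondary analyses on other populations if the analysis plan describes them. The visible SAP describes none for these endpoints.
- Protocol Section 9.4.3 and SAP Section 16.1 compare baseline characteristics with the parent population. The SAP makes this a visual comparison, and its text names the CLARIFY MS trials. Baseline tables cannot show differences in outcome.
- The Safety Analysis Population, read literally, covers everyone dosed in the parent study, but it is used for safety, and SAP Section 13 refers to it as the extension study's set.

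**Size of the effect.** The plan gives no figure to reproduce. Let *q* be the share of parent-treated participants who did not enter, *p* the event-free proportion in entrants, and *r* that in non-entrants.

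All-treated proportion = (1 − *q*)*p* + *qr*, so overstatement = *p* − [(1 − *q*)*p* + *qr*] = *q*(*p* − *r*).

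The documents give none of the three, so all are assumed. With *p* = 0.50:

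| *q* | *r* = 0.50 | *r* = 0.25 | *r* = 0 |
|---|---|---|---|
| 3% | 0 | 0.75 | 1.5 points |
| 10% | 0 | 2.5 | 5.0 points |
| 20% | 0 | 5.0 | 10.0 points |

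With *p* from 0.30 to 0.70 and *r* = 0, the range is 0.9 to 2.1 points at *q* = 3% and 6.0 to 14.0 points at *q* = 20%.

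For scale, the protocol plans 200 to 220 evaluable participants. The simple binomial 95% half-width at *p* = 0.50 is 1.96 × √(0.25/200) = 6.9 points, or 6.6 points at 220.

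**Relapse MCF.** Assume 0.40 relapses per entrant over 4 years, *q* = 10%, and non-entrants at *k* times that rate. All-treated mean = 0.40 × (0.9 + 0.1*k*): 0.40 at *k* = 1 and 0.44 at *k* = 2.

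**Would an all-treated analysis repair it?** This was simulated with 400,000 participants, exponential event times giving 50% event-free at 48 months in entrants, *q* = 10%, every non-entrant active, and rescue uniform over Months 3 to 24.

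| Non-entrants with an event recorded before leaving | Extension FAS | All treated, non-entrants without an event censored at exit | All treated, rescue counted as activity |
|---|---|---|---|
| none | 50.0% | 51.1% | 45.0% |
| half | 50.0% | about 48.0% | 45.0% |
| 80% | 50.0% | 46.2% | 45.0% |

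Under these assumptions the true all-treated value is 0.9 × 0.50 = 45.0%, so the last column is correct by construction. Plain censoring recovers only part of the gap. If no events were recorded it moves the wrong way, because non-entrants then add event-free time at risk and leave as censored.

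**The case against.** The strongest reply is that the two situations differ in kind. For the dropped endpoint the event itself bars entry, so the curve would be event-free to M24 by construction. For the retained endpoints a relapse, lesion or progression does not bar entry, and entrants' parent-study events count. Participants withdrawn from cladribine in the parent study may also join (Protocol Section 4.1). Dropping one endpoint and keeping the rest can therefore be defended. This stands: the bias is indirect and partial, and it is a reason to supplement the eight analyses, not to remove them.

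Several further points also have force:

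- The SAP hedges its statement of the exclusion, and Section 12 plans to present DMDs reported during the parent trial, so exclusion of rescued participants may not be complete.
- The protocol title, entry criteria and FAS definition let a careful reader infer the selection. They do not put it next to the results.
- The size is wholly assumed and includes zero. The upper figures need every non-entrant to have been active, although non-entry can have unrelated causes such as site participation or consent. At 10% non-entry the maximum of 5.0 points is below the sampling half-width. That half-width does not cover selection error, however.
- The parent study's own report may give non-entrants' parent-study outcomes. That would not correct the 3- and 4-year figures.
- Much of SAP Section 14 after 14.2.3 is redacted, so the absence of an all-treated analysis can be asserted only for the visible text.

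It can also be said that nothing in an exploratory single-arm extension names all treated participants as the target. But the SAP's own bias argument presupposes that benchmark, and an endpoint counted from first dose invites that reading.

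**Conclusion.** The concern holds and should be fixed. The SAP recognises a selection that depends on what happened after first dose, applies it to one endpoint, and leaves eight visible secondary endpoints with the same origin and analysis set unqualified. The expected direction is favourable to treatment if rescued non-entrants were more active than entrants.

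The omission is certain in the visible text; the size of any bias is not known. At an assumed 50% event-free estimate it lies between zero and 1.5, 5.0 or 10.0 points for assumed non-entry of 3%, 10% or 20%. The upper ends require that every non-entrant had activity. The primary endpoint and the other endpoints that start at M24 are not affected in this way.

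**What to change.** Keep the extension FAS results and make these changes to the SAP:

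1. Label every Day 1 result, including the one at the interim analysis, as conditional on having the parent-study data required for entry and on enrolling.
2. Repeat the eight Day 1 analyses on all participants treated in the parent study. Count their parent-study events, and censor non-entrants without an event at their last parent-study assessment. For the composites, use the earliest of last parent MRI, last parent EDSS and parent exit date, mirroring Section 14.2.1.
3. Because that censoring may be informative for rescued participants, add a sensitivity analysis that counts start of a rescue DMD as disease activity. Present it as a departure from the three-component NEDA-3 definition.
4. Report the number of non-entrants, their reasons where known, and their parent-study relapse, 6MCDP and MRI outcomes.
5. Correct the trial name in Section 16.1.

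The cost is SAP wording and programming, with no new data collection. Section 9 integrates parent data up to M24 as needed, and Section 4 says parent data not required will not be stripped out. Neither states that the datasets include people who never enrolled, so this must be confirmed. If they do not, items 1 and 5 need only wording. NEDA-3 to Year 4 and Day 1 time to first disease activity share start, events and censoring, so there are fewer than eight distinct derivations. The downsides are that the 3- and 4-year figures may look less favourable, and that people outside the Enrolled Set would appear in supplementary tables.
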